11. RESEARCH GOVERNANCE

11.1. Trial Organisation

Chief Investigator – The Chief Investigator will have overall responsibility for the design, coordination and management of the study. These include:

- Trial authorisation including responsibility for the protocol and obtaining approvals
- Ensuring that the trial is conducted according to Good Clinical Practice (GCP)
- Assessment of SAEs and providing a prompt response as to whether the SAE is a SUSAR.

Clinical Trials Unit –The Sponsor has delegated the responsibility for overall project management, data management and monitoring to the Scottish Clinical Trials Research Unit (SCTRU), based in Edinburgh. Responsibilities include:

- Assistance with completion of the IRAS form and MREC communication
- Production of trial specific documentation (i.e. CRFs)
- Assistance with site activation procedures within centres
- Data management
- Financial Management
- Monitoring
- Pharmacovigilance Reporting of serious adverse reaction (SAR)s / SUSARs

Statistical Analysis – [name], based at SCTRU, Edinburgh will undertake the final analysis arising for this study.

Sponsor – PHS will act as study sponsor. Central study co-ordination, data collection, monitoring and organisation of the data for the statistical analyses will be undertaken by SCTRU, which has processes in place to ensure that the study will not open to recruitment until appropriate approvals and authorisations have been obtained from the independent research ethics committee, and NHS Research and Development departments.

Local Project Teams – These will consist of Surgeons and/or Oncologists (responsible for introducing the patient to the study and ensuring eligibility and consent), Research Nurse (responsible for patient recruitment, obtaining consent and co-ordination of all aspects of data collection). Centres are specifically responsible for conducting the trial in accordance with the protocol, Standard Operating Procedures (SOPs), the trial agreement and Good Clinical Practice.

Trial Steering Committee (TSC) – The Trial Steering Committee (TSC), including members of the research team and an independent Chair, will be responsible for the progress and conduct of the study and convene after the scheduled DMC meetings.

Trial Management Group (TMG) – A Trial Management Group (TMG) will meet approximately every 6 months to oversee the operational aspects of the trial. Responsibilities will be outlined within the TMG charter.

The TMG will include consultant neurologists who will work as part of the group to review source documents (or event descriptions) for 10% of all identified seizures. All seizures will be assessed utilising a standard seizure definition (definition of a seizure described in section 2.4).

Any discrepancy in classification between the TMG review and the original investigator decision will be recorded. Numbers of discrepancies will be highlighted to the Data Monitoring Committee.

Data Monitoring and Ethics Committee (DMC) – A Data Monitoring and Ethics Committee will convene 6 monthly initially, and annually thereafter, to review all data including adverse events and develop a stopping policy for the trial, if necessary. Specific issues that will be looked at include: tolerability of initial dose, dose reductions, toxicities (including interaction of the mild increased bleeding risk) & review schedules. There will be an extra meeting of the committee after 50% recruitment.

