2.4. Definition of Seizure

If the patient has a seizure they should contact their treating team. The patient should be reviewed by a neurologist to confirm whether a seizure has taken place.

For study purposes, confirmed seizures will include any of the following:

- 1. Simple partial seizures:
 - a) with motor symptoms: focal motor movements, versive/postural movements
 - b) with sensory symptoms: olfactory sensations
 - c) with autonomic signs
 - d) with psychic symptoms (e.g. déjà vu, jamais vu)
- 2. Complex partial seizures
 - a) with impairment of consciousness only
 - b) with impairment of consciousness plus automatisms (lip smacking, fumbling, etc.)
- 3. Partial seizures with secondarily generalized seizures
 - a) Unconsciousness with generalised clonic movements
 - b) Unconsciousness with generalised tonic spasm, without clonic movements
 - c) Unconsciousness or staring with one of the following preceding symptoms perceived by the patient:
 - A rising feeling from the abdomen to the throat
 - Smelling of odd scents
 - Stiffening or convulsions in the face or limb(s)
 - Turning the head to one side.

Excluded attacks are those deemed by the treating physician not to be epileptic seizures.

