3. TRIAL DESIGN

3.1. General Design

This is a two arm, multicentre phase III randomised trial of prophylactic anti-epileptic drug (Levetiracetam) versus no anti-epileptic drug (AED) (comparator) in patients with suspected cerebral glioma.

Randomly assigned - 1:1 basis

This will not be a blinded study and will not have placebo control and as such will be a "real world" study of prophylactic AED vs. no AED. The reasons for the lack of placebo arm include; real world nature of the study, patient involvement feedback on the design with specific reference to value of a placebo arm; over-encapsulation as levetiracetam capsules are large; and cost of the study.

804 patients will be recruited and randomised into one of two arms:

- **Group 1**: Levetiracetam 500mg twice daily for 2 weeks, then increasing to 750mg twice daily thereafter for 1 year. Patients should have a minimum of 2 doses of 500mg prior to surgery. (In those with moderate chronic kidney disease stage 3 estimated Glomerular Filtration Rate (eGFR 30-59 mL/min/1.73 m²) a starting dose of 250mg twice a day for 2 weeks, then increasing to 500mg twice a day thereafter).
- **Group 2**: no AED treatment (standard care)

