The relative changes in health related quality of life (HRQoL) resulting from the physical and psychological benefit together with any harms associated with each treatment strategy will be based upon responses to the EQ-5D-5L, which will be administered face to face at pre surgery (baseline), 3 months, 6 months, 9 months and 12 months post randomisation. The Proxy 1 version will also be completed by the patients Carer if possible at each visit. In order to account for the short term decrement associated with having an acute seizure, the EQ-5D-5L Telephone version will also be collected through a telephone interview with a research nurse when the participant experiences their first episode of seizure like symptoms during the trial period. Separately, data will be collected to determine whether the suspected seizure was a seizure or not. Only utilities of events shown as seizures will be used in the assessment of cost-effectiveness.

The EQ-5D-5L is a standardised and validated generic instrument that is widely used in economic evaluations, and has been validated in many patient populations and using numerous modes of administration. Proxy versions of the EQ-5D-5L and a face to face version will be available to help the patient/carer as described in Section 2.5. The responses to the EQ-5D-5L will be converted into health state valuations using the recently published value set [⁴⁶].

Although the descriptive system for the EQ-5D-5L has been validated by National Institute for Health and Care Excellence (NICE), to date the valuation set has not. Therefore, as a sensitivity analysis, the responses to the EQ-5D-5L will also be converted into health state valuations by mapping the EQ-5D-5L descriptive data onto the EQ-5D-3L value set using the

mapping function validated by NICE [⁴⁷]. Both sets of utility values will then be combined with the study participant's mortality to estimate QALYs for each trial participant, using the 'under the curve' approach [⁴⁸]. A mean QALY per intervention arm will then be estimated.

Data analysis

Once mean costs and QALYs have been calculated, these values will be presented for the two randomised group, as well as incremental mean costs and QALYs calculated with the incremental cost per QALY gained at 12 months. As the trial follow up period is 12 months, costs and effects will not be discounted.

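### The only stated central check of the open-label primary outcome covers about 8 accepted seizures, is not stated to be masked, and leaves out events rejected by a physician who knows the arm

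*Protocol*

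**What the plan says.** Protocol section 3.1 states: "This will not be a blinded study and will not have placebo control". The primary analysis (section 7.3.1) is a logistic regression on whether a seizure occurred in the first year, so it depends on how each suspected event is classified.

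Section 2.4 covers local classification in two sentences. One is "The patient should be reviewed by a neurologist to confirm whether a seizure has taken place". The other, which closes the section, is "Excluded attacks are those deemed by the treating physician not to be epileptic seizures". Masking is not mentioned for either step, and the section does not say whose view prevails if the two clinicians differ.

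Section 11.1 gives the central check. The Trial Management Group (TMG) includes consultant neurologists who "review source documents (or event descriptions) for 10% of all identified seizures". On the outcome of that review it says "Any discrepancy in classification between the TMG review and the original investigator decision will be recorded" and "Numbers of discrepancies will be highlighted to the Data Monitoring Committee". It does not mention masking, how the 10% is chosen, review of events judged not to be seizures, a count by arm, or what a discrepancy leads to.

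Suspected events are captured whether or not they are confirmed. The visit schedule in section 4.3 has a column for a reported suspected seizure, and section 7.3.5 says "Separately, data will be collected to determine whether the suspected seizure was a seizure or not".

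**The concern.** The seizure definition in section 2.4 includes focal sensory, autonomic and psychic events, which call for judgement. The person who may exclude an attack knows the allocation. Two features of the protocol make a difference between arms plausible. Section 1.5 lists hallucination, panic attacks, memory impairment and prickling sensation among the side effects of levetiracetam, so a doubtful episode has a ready alternative explanation in one arm only. Section 3.4 attaches a consequence to a confirmed seizure that exists only in the levetiracetam arm, namely removal from study drug.

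If doubtful events are rejected more readily in the levetiracetam arm, its observed rate falls and the odds ratio moves in favour of the drug. A review that starts from identified seizures cannot find those events. For the opposite error, events wrongly accepted, the review can find some, but the number examined is very small.

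**Working it through.** **Inputs from section 7.1:** control risk 20%, levetiracetam risk 10%, power 90%, two-sided 5%, 1:1 allocation, 80 seizures required, attrition 24.8% and 12%. From section 11.1: 10% of identified seizures reviewed. The misclassification rates below are assumptions, because the documents give none.

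**1. The plan's own figures.** With pooled variance under the null and no continuity correction:

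n per arm = [1.960 × √(2 × 0.15 × 0.85) + 1.282 × √(0.20 × 0.80 + 0.10 × 0.90)]² / 0.10² = (0.990 + 0.641)² / 0.01 ≈ 266, so 532 in total.

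Seizures: 266 × 0.20 + 266 × 0.10 = 53.2 + 26.6 = 79.8, rounded to 80. Inflated total: 532 / (0.752 × 0.88) = 803.9, rounded to 804. All agree with the protocol; the sample size is not in dispute.

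**2. Size of the check.** 10% of 80 is 8 records. At the planned rates these split as 8 × 53.2/79.8 ≈ 5 control and 8 × 26.6/79.8 ≈ 3 levetiracetam. If all 804 patients were evaluable there would be 402 × 0.30 ≈ 121 seizures and 12 or 13 records.

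**3. What 8 records can show about wrongly accepted events.**
- Chance of at least one discrepancy: 1 − 0.95⁸ = 34% if 5% of accepted seizures are false, and 1 − 0.90⁸ = 57% if 10% are. With 13 records the latter is 75%.
- With no discrepancy in 8, the one-sided 95% upper limit for the false share is 1 − 0.05^(1/8) = 31%. By arm it is 45% for 0 of 5 and 63% for 0 of 3.

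The sample may reveal some errors, but it cannot compare the arms.

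**4. Wrongly rejected events.** These are not in the sampling frame on its natural reading, so the chance of finding one is nil. To gauge the effect, suppose the true risk is 20% in both arms and a share r of true seizures is rejected in the levetiracetam arm only, giving an observed risk of 0.20(1 − r) there. The rejection probability comes from the same two-proportion normal approximation. For r = 10% at 266 per arm:
- pooled SE = √(0.19 × 0.81 × 2/266) = 0.03402; unpooled SE = √((0.16 + 0.1476)/266) = 0.03401
- tail favouring levetiracetam: 1 − Φ((1.960 × 0.03402 − 0.02)/0.03401) = 8.5%
- other tail: 0.5%; total 9.0%

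| Share rejected, levetiracetam arm only | Observed risk | Apparent odds ratio | Type I error, 266 per arm | Type I error, 402 per arm |
|---|---|---|---|---|
| 0 | 20% | 1.00 | 5.0% | 5.0% |
| 5% | 19% | 0.94 | 6.0% | 6.5% |
| 10% | 18% | 0.88 | 9.0% | 11% |
| 20% | 16% | 0.76 | 22% | 31% |

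**5. The other direction.** If the true risks are 20% and 10% and the rejections fall in the control arm only, power at 266 per arm drops from 90% to 76% (10% rejected) or 54% (20% rejected).

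**The case against.** The strongest reply is that section 2.4 already puts a neurologist in front of the patient before classification, so rejected events are meant to have specialist review; that the TMG's responsibilities are to be set out in a charter not shown here; and that sensitivity analyses of endpoint classification belong in the statistical analysis plan (SAP), which is also not shown. All of this is fair, and it rules out several stronger statements that a reader might infer.

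- *That the reviewers are unmasked.* The protocol is silent on this. All that can be said is that masking is not stated.
- *That rejected events are never reviewed.* Local neurologist review is intended for them. What is missing is any stated central review, and the local step is worded as something that should happen.
- *That discrepancies have no effect on the data.* The protocol states only recording and counting. A charter or SAP could add more.
- *That the check cannot see error at all.* It can see some false positives. Suppose the true risk is 15% in both arms and labelling adds 3 points in one. Then 3/33 = 9% of accepted events are false, and reviewing 9 of about 88 events (266 per arm) gives a 58% chance of meeting at least one.

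Two further limits stand. The word identified is not defined; reading it as accepted by the investigator is natural, because the comparison is with the investigator's decision, but it is an inference. And the type I errors above follow wholly from assumed rejection rates; at 5% the effect is small.

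The reply does not remove the main point. Section 2.4 lets the treating physician exclude an attack without stating that the neurologist must agree. Section 11.1 itself fixes what is sampled and what follows. Section 3.1 gives reasons for having no placebo, and none of them bears on masking the event review. The quarterly line listing in section 5.4 includes seizures but serves safety review.

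**Conclusion.** The point holds as a weakness in endpoint quality control and does not show that the result will be biased. As written, the central check examines about 8 records, about 5 control and 3 levetiracetam. It is not stated to be masked and most naturally excludes events rejected locally. It is too small to show a difference between arms in false positives and is blind to true seizures rejected by a physician who knows the arm. If such rejection occurred in the levetiracetam arm only, at an assumed 5% to 20%, the two-sided type I error would be about 6% to 22% at 266 per arm, or 6.5% to 31% at 402 per arm. This assumes 20% true risk in both arms and no compensating error in the control arm. The change is worth making because it is cheap and the suspected events are already recorded.

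**What to change.** In section 11.1:
- remove allocation and anti-epileptic drug details from the event descriptions before the TMG neurologists see them;
- draw the reviewed sample from all reported suspected events, rejected ones included, stratified by arm and local classification;
- report discrepancies to the Data Monitoring Committee by arm.

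In section 2.4, reconcile the two sentences so that the neurologist's classification governs whether an event is excluded from the endpoint.

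As a supporting step, add a sensitivity analysis of the primary outcome that counts every reported suspected seizure as an event, if the SAP does not already have one. It should be read with care, since patients know their allocation and their reporting may itself differ by arm.

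Cost: redaction work, one extra analysis, and possibly some local neurologist review where it is not now done. If the review load stays the same, fewer accepted seizures will be reviewed, because part of the load moves to rejected events. The protocol gives no expected number of suspected events, so that trade cannot be sized. For scale, reviewing every accepted seizure would mean about 80 records, or about 121 if all 804 patients were evaluable. That is an option and is not needed for the change proposed.

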availability of an intravenous preparation is yet another advantage. It has been demonstrated effective as adjunctive therapy for refractory partial-onset seizures, primary generalized tonicclonic seizures, and myoclonic seizures of juvenile myoclonic epilepsy. In addition, it was found equivalent to controlled release carbamazepine as first-line therapy for partial-onset seizures, both in efficacy and tolerability. Its main adverse effects in randomised adjunctive trials in adults have been somnolence, asthenia, infection, and dizziness.

There is some evidence to suggest that levetiracetam may be neuro-protective in brain injury [²⁶] and that it may be associated with improved cognition in brain tumour patients [²⁷]. Lastly, there is some evidence that levetiracetam may inhibit malignant glioma cell proliferation and increase glioma cell sensitivity to the alkylating agent temozolomide [²⁸].

Side effects of Levetiracetam

AED use is associated with many potential side effects that can have a negative impact on a patient's quality of life. Side effects of levetiracetam can be:

- Affecting more than 1 in 10 people at varied levels of severity are: sleepiness, headache, and running/blocked nose.
- Affecting between 1 in 10 and 1 in 100 people- at varied levels of severity are: off food, low mood or changes in behaviour, anxiety, poor sleep, dizziness, gastrointestinal symptoms (indigestion, loose stools).
 - Affecting between 1 in 100 and 1 in 1000 people weight increase or decrease, change in levels of blood cells, suicidal thoughts, hallucination, mood swings, panic attacks, memory impairment, prickling sensation, coordination problems, amnesia, blurred/double vision, skin conditions, abnormal liver function, muscular weakness and myalgia.
 - Affecting between 1 in 1000 and 1 in 10000 people– infection, changes to normal blood levels, hypersensitivity, suicide, personality disorder, uncontrolled involuntary movement, gait disturbance (walking disorder), encephalopathy, delirium, pancreatitis, liver failure, kidney problems, skin disorders, muscle problems, increased delay between heartbeats on Electrocardiogram, seizures aggravated.

Complete blood cell counts are advised in patients experiencing important weakness, pyrexia, recurrent infections or coagulation disorders.

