5. PHARMACOVIGILANCE

5.1. Definitions

Adverse Reaction (AR): All noxious and unintended responses related to a study treatment or procedure should be considered adverse drug reactions.

Serious Adverse Event (SAE): Any untoward medical occurrence in a patient that

- a) Results in death
- b) Is life-threatening
- c) Requires hospitalisation or prolongation of existing hospitalisation
- d) Results in persistent or significant disability or incapacity
- e) Consists of a congenital anomaly or birth defect
- f) Is otherwise considered to be medically significant by the investigator (e.g. intensive treatment in an emergency room or at home for allergic bronchospasm or blood dyscrasias).

The term "life-threatening" refers to an event in which the patient was at risk of death at the time of the event; it does not refer to an event which hypothetically might have caused death if it were more severe.

Hospitalisations planned prior to enrolment in the trial or for social reasons should not normally be considered as SAEs unless the hospitalisation has to be prolonged. Treatment in an emergency room of less than 24 hours or on an out-patient basis that does not meet any other serious criteria should not be considered as an SAE.

Suspected Unexpected Serious Adverse Reaction (SUSAR): A suspected unexpected serious adverse reaction (SUSAR) is an adverse reaction that is classified as serious and it is thought to be caused by a study treatment or procedure. Expected events are detailed within the Summary of Product Characteristics (SmPC). The nature, severity or outcome of this adverse reaction must not be consistent with SmPC for the treatment or procedure.

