5.3. Recording and Reporting of Adverse Reactions

All related Adverse Reactions will be recorded in the Case Report Form and graded according to Common Terminology Criteria for Adverse Events (CTCAE) version 5. Any Adverse Reaction considered unrelated will not be recorded.

All adverse reactions that occur after the signing of written informed consent and within 30 days after the final study treatment will be recorded on the appropriate eCRF page. The exception to this would be any event occurring after signing the informed consent and prior to commencing study treatment that is considered unrelated to trial procedures. In addition, any events occurring more than 30 days after final study treatment that are deemed to be related to the study drug should be notified to PHS as detailed in section 5.4.

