5.5. Recording and Reporting of Serious Adverse Events

All serious adverse events (not subject to modified safety reporting in section 5.4) that occur after the signing of written informed consent and within 30 days after the final study treatment will be recorded on the SAE report form. Study treatment should be considered any study

activity from informed consent until the final follow up visit or end of final medication (if on IMP arm and in receipt of taper pack). The CTCAE grading will also be captured.

The exception to this would be any event occurring after signing the informed consent and prior to commencing study activity that is considered unrelated to trial procedures. In addition, for patients on IMP arm any events occurring more than 30 days after final study treatment that are deemed to be related to the study drug should be notified to PHS as above.

The SAE case report form must be completed on the Trial eCRF and signed by the Principal Investigator of the centre involved within 24 hours of first becoming aware of the event.

All initial SAE reports should contain the following minimum information:

- Reporter information
- At least one subject identifier (trial number/patient initials)
- Event term
- Assessment of relatedness
- Suspect drug or procedure
- Serious criteria

Sites should email [contact] to notify PHS that an SAE has been reported.

All SAEs for patients on the IMP arm will be forwarded to the CI by PHS for assessment of expectedness against the SmPC. Any SAE that is deemed to be both related and unexpected (i.e. a SUSAR) will be notified to the appropriate Competent Authorities and Research Ethics Committee within 7 days of becoming aware of the event for fatal or life threatening events and 15 days for all other serious events.

Hospitalisations planned prior to enrolment in the trial should not normally be considered as SAEs unless the hospitalisation has to be prolonged. Treatment in an emergency room of less than 24 hours or on an out-patient basis that does not meet any other serious criteria should not be considered as an SAE.

Please refer to SPRING instruction manual for sites for reporting instructions.

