All patients will be informed of the aims of the study, the possible adverse events, the procedures and possible hazards to which they will be exposed, and the mechanism of treatment allocation. They will be informed as to the strict confidentiality of their patient data, but that their medical records may be reviewed for trial purposes by authorised individuals other than their treating physician. It will be emphasized that the participation is voluntary and that the patient is allowed to refuse further participation in the protocol whenever they want. This will not prejudice the patient's subsequent care.

Documented informed consent must be obtained for all patients included in the study before they are enrolled or randomised. This must be done in accordance with the national and local regulatory requirements and must conform to guidelines on Good Clinical Practice.

All patients must be able to provide informed consent on joining the trial and will have the option to consent to remain in the trial and on IMP (if applicable) should they suffer a decline in cognitive ability at any point during the trial.

All Patient Information Sheets & Informed Consent Forms will be version controlled and dated and this information will always be stated in any communication with ethics committees.

Carers will also be consented to ensure they are able and willing to assist/complete EQ-5D-5L and other questionnaires as required. If a new carer attends a visit and can complete the EQ-5D-5L then they will be consented at that time.

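### Bleeding is a named DMC topic, but bleeds below the SAE threshold are in practice recorded only on levetiracetam, so only serious bleeding can be compared fairly between arms

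*Protocol*

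**What the plan says.** - **DMC remit (protocol, section 11.1).** The committee reviews all data, adverse events included. Among its specific topics are "toxicities (including interaction of the mild increased bleeding risk". The text gives no rate or source and does not say what the interaction is with. This is the only mention of bleeding in the protocol.
- **Timing of treatment (section 3.1).** The drug is started before brain surgery: "Patients should have a minimum of 2 doses of 500mg prior to surgery".
- **Safety background (section 1.5).** The summary reads: "Its main adverse effects in randomised adjunctive trials in adults have been somnolence, asthenia, infection, and dizziness". The nearest text to bleeding is: "Complete blood cell counts are advised in patients experiencing important weakness, pyrexia, recurrent infections or coagulation disorders". Section 5.2 leaves the list of expected reactions to the SmPC.
- **Non-serious events (sections 5.1 and 5.3).** A reaction is defined by its link to the trial: "All noxious and unintended responses related to a study treatment or procedure should be considered adverse drug reactions". The recording rule is: "Any Adverse Reaction considered unrelated will not be recorded".
- **Serious events (section 5.5).** The rule is wider: "All serious adverse events (not subject to modified safety reporting in section 5.4) that occur after the signing of written informed consent" go on the SAE form, related or not. For this purpose study treatment means any study activity from consent to the last follow-up visit, so controls are covered.
- **Analysis (section 7.3.2).** CTCAE grades of the tabulated adverse events are compared between arms with a Mann-Whitney U test.

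**The concern.** A safety topic that the protocol itself singles out should rest on data collected in the same way in both arms. Here collection depends on seriousness. Above the SAE threshold, cause does not matter. Below it, an event enters the data only if someone attributes it to the trial. In an open-label trial with an untreated control group, the site always knows whether there is a drug to blame.

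The DMC could therefore see more recorded bleeds on levetiracetam when the true rates are equal, and could not tell that from a real excess. The same events feed the between-arm comparison of grades. Because the remit does not say what the bleeding risk is, sites also have nothing in the protocol to guide attribution, so the amount of bias may differ between sites.

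**Working it through.** The protocol states no bleeding figure, so there is none to reproduce. The check is to trace which bleeds are recorded in which arm and then illustrate the consequence.

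**Step 1: route into the data**

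| Type of bleed | Levetiracetam | Control |
|---|---|---|
| Fatal, life-threatening, disabling, or prolonging admission | Recorded as SAE (5.1, 5.5) | Recorded as SAE (5.1, 5.5) |
| Not serious, judged related | Recorded (5.1, 5.3) | No drug to relate it to; surgery was planned regardless of the trial (3.2) |
| Not serious, judged unrelated | Not recorded (5.3) | Not recorded (5.3) |

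Only the middle row differs by arm, and it can only add to the levetiracetam count.

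**Step 2: size, on assumed inputs**

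- n = 402 per arm (section 7.1).
- r = true bleeding rate, equal in both arms. Assumed 3-10%.
- s = share of bleeds that are serious. Assumed 0.30-0.60.
- q = probability that a non-serious bleed on levetiracetam is judged related. Assumed 0.25-0.50. In controls it is taken as 0.

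Recorded on levetiracetam: n × r × [s + (1 − s)q]. Recorded on control: n × r × s.

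Ratio = 1 + (1 − s)q / s. The rate r cancels, so the false ratio depends only on s and q.

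At r = 5% there are 402 × 0.05 = 20.1 true bleeds per arm:

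| s | q | Recorded, levetiracetam v control | Ratio |
|---|---|---|---|
| 0.30 | 0.25 | 9.5 v 6.0 | 1.58 |
| 0.30 | 0.50 | 13.1 v 6.0 | 2.17 |
| 0.60 | 0.25 | 14.1 v 12.1 | 1.17 |
| 0.60 | 0.50 | 16.1 v 12.1 | 1.33 |

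The counts scale with r. In the second row they are 7.8 v 3.6 at 3% and 26.1 v 12.1 at 10%, with the same ratio of 2.17. Restricted to SAEs, both arms record n × r × s and the ratio is 1.0.

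**Step 3: the grade comparison in section 7.3.2**

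If patients with no recorded bleed take the lowest rank, the missing control bleeds push the test against levetiracetam. If only recorded events were ranked, the distortion could run the other way, because the recorded control bleeds would be the serious ones. Either way, the all-grade comparison reflects the recording rule as well as the drug.

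**The case against.** The strongest answer is that the bleeding that matters most is covered. Section 5.5 records serious events in both arms regardless of cause, section 5.1 counts prolonged hospitalisation as serious, and the DMC sees all data. This stands. A reader might infer that the DMC has no fair comparison of bleeding at all; the documents do not support that.

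Other stronger readings also fail:

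- **The visit schedule shows that bleeding is not collected after surgery.** The post-surgery column in section 4.3 holds only an MRI, but the schedule has no adverse-event row in any column, so its silence proves nothing.
- **Section 5.4 hides bleeds.** It exempts progressive neurological deficit, not a diagnosed haemorrhage. The exemption applies to both arms, and exempted events still appear in a quarterly listing. A bleed reported by its presentation could be classed there, which justifies a clarifying line but does not show loss of data.
- **The safety sections deny the risk.** Section 1.5 lists main effects and refers to coagulation disorders. Its statement on interactions concerns other drugs. Silence in a summary is not denial.
- **Patients are not told.** Section 10.2 says "All patients will be informed of the aims of the study, the possible adverse events". The information sheets are not shown, so no gap can be claimed. The same holds for the eCRF and the DMC charter, either of which may contain a bleeding item.
- **The DMC will see 12 v 6.** At 3% with half of the bleeds serious, 402 × 0.03 = 12.1 v 6.0 requires every non-serious levetiracetam bleed to be judged related. With 25-50% attribution the figures are 7.5 to 9.0 v 6.0.

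Two points remain open. Section 4.2 says that all patient-reported events will be recorded, but this sits badly with section 5.3 and would not capture a bleed found only on a scan or in surgical notes. Sites could also read the operation as a study procedure, which would give controls a route, but nothing tells them to. Finally, section 11.1 does not mention surgery, so the link to post-operative bleeding is an inference; the remedy should not be limited to that period.

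**Conclusion.** The point holds in a limited form. The DMC is given a bleeding topic that no other section names or explains, and the recording rule makes counts of non-serious bleeding depend on arm. Serious bleeding can be compared; all-grade bleeding cannot be compared without bias against levetiracetam.

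The size is unknown. The ratios of roughly 1.2 to 2.2 for all grades and 1.0 for SAEs rest on assumed shares of serious bleeds and of attribution, on equal true rates, and on no non-serious bleed being recorded in controls. None of these comes from the protocol. The direction follows from sections 5.1 and 5.3 with an untreated comparator. The primary efficacy comparison is unaffected. This is an inexpensive improvement to safety recording, not a flaw that undermines the trial.

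**What to change.** 1. In section 11.1 and the safety sections, state what the bleeding risk and the interaction refer to. Keep the topic in the DMC remit.
2. Record haemorrhage in both arms regardless of cause or seriousness, including after surgery, with its date and whether it was serious, from routine notes and scans.
3. State in section 5.4 that a diagnosed haemorrhage does not fall under the exemption for progressive neurological deficit.
4. Tabulate haemorrhage by arm for the DMC, separating serious from non-serious.
5. Until this is in place, base any between-arm comparison of bleeding on SAEs only, and say so where section 7.3.2 compares grades.

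The cost is one data item per patient, a few clarifying lines and one table. No visit, test or procedure is added. The downside is slightly more data entry. If the eCRF already holds such an item, only the wording changes are needed.
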